8.3.2 Vital Signs

Body temperature, heart rate, respiratory rate, and blood pressure will be assessed.

Vital sign measurements should be preceded by at least 5 minutes of rest for the participant in a quiet setting without distractions.

8.3.3 Clinical Safety Laboratory Assessments

Refer to Appendix 2 for the list of clinical laboratory tests to be performed and to the SoA for the timing and frequency.

- The investigator or medically qualified designee (consistent with local requirements) must review the laboratory report, document this review, and record any clinically relevant changes occurring during the study in the AE section of the CRF. The laboratory reports must be filed with the source documents. Clinically significant abnormal laboratory findings are those which are not associated with the underlying disease, unless judged by the investigator to be more severe than expected for the participant's condition.
- All protocol-required laboratory assessments, as defined in Appendix 2, must be conducted in accordance with the laboratory manual and the SoA.
- If laboratory values from nonprotocol-specified laboratory assessments performed at the institution's local laboratory require a change in study participant management or are considered clinically significant by the investigator (eg, SAE or AE), then the results must be recorded in the appropriate CRF (eg, SLAB).
- For any laboratory tests with values considered clinically significantly abnormal during participation in the study or within 14 days after the last dose of study intervention, every attempt should be made to perform repeat assessments until the values return to normal or baseline or if a new baseline is established as determined by the investigator.

8.3.4 Pregnancy Testing

- Pregnancy testing:

Pregnancy testing requirements for study inclusion are described in Section 5.1.

Pregnancy testing should be conducted at screening (serum or urine) and on Day 29 (serum), approximately 24 days after the last dose of study intervention.

Additional serum or urine pregnancy tests may be performed, as determined necessary by the investigator or required by local regulation, to establish the absence of pregnancy at any time during the subject's participation in the study.

8.4 Adverse Events, Serious Adverse Events, and Other Reportable Safety Events

The definitions of an AE or SAE, as well as the method of recording, evaluating, and assessing causality of AE and SAE and the procedures for completing and transmitting AE, SAE, and other reportable safety event reports can be found in Appendix 3.

Adverse events, SAEs, and other reportable safety events will be reported by the participant (or, when appropriate, by a caregiver, surrogate, or the participant's legally authorized representative).

The investigator and any designees are responsible for detecting, documenting, and reporting events that meet the definition of an AE or SAE as well as other reportable safety events. Investigators remain responsible for following up AEs, SAEs, and other reportable safety events for outcome according to Section 8.4.3.

The investigator, who is a qualified physician, will assess events that meet the definition of an AE or SAE as well as other reportable safety events with respect to seriousness, intensity/toxicity and causality.

8.4.1 Time Period and Frequency for Collecting AE, SAE, and Other Reportable Safety Event Information

All AEs, SAEs, and other reportable safety events that occur after the participant provides documented informed consent but before intervention randomization must be reported by the investigator if the participant is receiving placebo run-in or other run-in treatment, if the event causes the participant to be excluded from the study, or is the result of a protocol-specified intervention, including but not limited to washout or discontinuation of usual therapy, diet, or a procedure.

From the time of intervention randomization through 14 days following cessation of study intervention, all AEs, SAEs, and other reportable safety events must be reported by the investigator.

Additionally, any SAE brought to the attention of an investigator at any time outside of the time period specified in the previous paragraph must be reported immediately to the Sponsor if the event is considered related to study intervention.

Investigators are not obligated to actively seek AEs or SAEs or other reportable safety events in former study participants. However, if the investigator learns of any SAE, including a death, at any time after a participant has been discharged from the study, and he/she considers the event to be reasonably related to the study intervention or study participation, the investigator must promptly notify the Sponsor.

All initial and follow-up AEs, SAEs, and other reportable safety events will be recorded and reported to the Sponsor or designee within the time frames as indicated in [Table 3](#).

Exception: A positive pregnancy test at the time of initial screening is not a reportable event unless the participant has received study intervention.

Table 3 Reporting Time Periods and Time Frames for Adverse Events and Other Reportable Safety Events

Type of Event	Reporting Time Period: Consent to Randomization/Allocation	Reporting Time Period: Randomization/Allocation through Protocol-specified Follow-up Period	Reporting Time Period: After the Protocol-specified Follow-up Period	Time Frame to Report Event and Follow-up Information to Sponsor:
NSAE	Report if: - due to protocol-specified intervention - causes exclusion - participant is receiving placebo run-in or other run-in treatment	Report all	Not required	Per data entry guidelines
SAE	Report if: - due to protocol-specified intervention - causes exclusion - participant is receiving placebo run-in or other run-in treatment	Report all	Report if: - drug/vaccine related. (Follow ongoing to outcome)	Within 24 hours of learning of event
Pregnancy/ Lactation Exposure	Report if: - participant has been exposed to any protocol-specified intervention (eg, procedure, washout or run-in treatment including placebo run-in) Exception: A positive pregnancy test at the time of initial screening is not a reportable event.	Report all	Previously reported – Follow to completion/termination; report outcome	Within 24 hours of learning of event
ECI (require regulatory reporting)	Report if: - due to intervention - causes exclusion	Report - Potential DILI - Require regulatory reporting	Not required	Within 24 hours of learning of event
ECI (do not require regulatory reporting)	Report if: - due to intervention - causes exclusion	Report - non-DILI ECIs and those not requiring regulatory reporting	Not required	Within 5 calendar days of learning of event
Cancer	Report if: - due to intervention - causes exclusion	Report all	Not required	Within 5 calendar days of learning of event (unless serious)
Overdose	Report if: - receiving placebo run-in or other run-in medication	Report all	Not required	Within 5 calendar days of learning of event

DILI=drug-induced liver injury; ECI=event of clinical interest; NSAE=nonserious adverse event; SAE=serious adverse event

8.4.2 Method of Detecting AEs, SAEs, and Other Reportable Safety Events

Care will be taken not to introduce bias when detecting AEs and/or SAEs and other reportable safety events. Open-ended and nonleading verbal questioning of the participant is the preferred method to inquire about AE occurrence.

8.4.3 Follow-up of AE, SAE, and Other Reportable Safety Event Information

After the initial AE/SAE report, the investigator is required to proactively follow each participant at subsequent visits/contacts. All AEs, SAEs, and other reportable safety events, including pregnancy and exposure during breastfeeding, ECIs, cancer, and overdose will be followed until resolution, stabilization, until the event is otherwise explained, or the participant is lost to follow-up (as defined in Section 7.3). In addition, the investigator will make every attempt to follow all nonserious AEs that occur in randomized participants for outcome. Further information on follow-up procedures is given in Appendix 3.

8.4.4 Regulatory Reporting Requirements for SAE

Prompt notification (within 24 hours) by the investigator to the Sponsor of SAE is essential so that legal obligations and ethical responsibilities towards the safety of participants and the safety of a study intervention under clinical investigation are met.

The Sponsor has a legal responsibility to notify both the local regulatory authority and other regulatory agencies about the safety of a study intervention under clinical investigation. The Sponsor will comply with country-specific regulatory requirements and global laws and regulations relating to safety reporting to regulatory authorities, IRB/IECs, and investigators.

Investigator safety reports must be prepared for SUSARs according to local regulatory requirements and Sponsor policy and forwarded to investigators as necessary.

An investigator who receives an investigator safety report describing an SAE or other specific safety information (eg, summary or listing of SAE) from the Sponsor will file it along with the IB and will notify the IRB/IEC, if appropriate according to local requirements.

8.4.5 Pregnancy and Exposure During Breastfeeding

Although pregnancy and infant exposure during breastfeeding are not considered AEs, any pregnancy or infant exposure during breastfeeding in a participant (spontaneously reported to the investigator or their designee), including the pregnancy of a male participant's female partner, that occurs during the study are reportable to the Sponsor as described in Section 8.4.1.

All reported pregnancies must be followed to the completion/termination of the pregnancy.

Any pregnancy complication will be reported as an AE or SAE.

The medical reason (example: maternal health or fetal disease) for an elective termination of a pregnancy will be reported as an AE or SAE. Prenatal testing showing fetus will be born

with severe abnormalities/congenital anomalies that lead to an elective termination of a pregnancy will be reported as an SAE for the fetus.

Pregnancy outcomes of ectopic pregnancy, spontaneous abortion, missed abortion, benign hydatidiform mole, blighted ovum, fetal death, intrauterine death, miscarriage, and stillbirth must be reported as serious events (Important Medical Events). If the pregnancy continues to term, the outcome (health of infant) must also be reported.

8.4.6 Disease-related Events and/or Disease-related Outcomes Not Qualifying as AEs or SAEs

Certain efficacy endpoints including hospitalizations and mortality must be collected throughout the study (ie, during both treatment and follow-up). From the time of randomization through 14 days following cessation of study intervention, these events must be reported as described in Section 8.4.1. New hospitalizations and/or deaths that occur after 14 days following cessation of treatment must continue to be assessed for seriousness and causality. However, they must only be reported to the Sponsor within 24 hours as new SAEs if there is evidence to suggest a causal relationship between the study intervention and the SAE.

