8.1.8.1 Timing of Dose Administration

Participants will take the appropriate number of capsules of study intervention (as described in the study intervention administration instructions) Q12H (± 2 hours) for 10 doses. Study intervention can be administered without regard to food. Refer to Section 8.6.1 regarding PK collection.

- For participants that begin dosing in the morning on Day 1, the EOT visit will occur on Day 5. PK specimens will be collected at the EOT visit in association with the 9th dose, and the final 10th dose will occur in the evening on Day 5.
- For participants that begin dosing in the evening on Day 1, the EOT visit will occur on Day 6. PK specimens will be collected at the EOT visit in association with the 10th dose on Day 6.

As outlined in the SoA, all efforts should be made to administer the first dose on Day 1 (randomization), but administration of the first dose must occur within 24 hours of randomization; therefore it is possible that dosing may not begin until Day 2.

- For participants that begin dosing in the morning on Day 2, the EOT visit will occur on Day 6. PK specimens will be collected at the EOT visit in association with the 9th dose, and the final 10th dose will occur in the evening on Day 6.

- For participants that begin dosing in the evening on Day 2, the EOT visit will occur on Day 7. PK specimens will be collected at the EOT visit in association with the 10th dose on Day 7.

If the EOT visit occurs on Day 6, no additional visit is required on Day 5. And if the EOT visit occurs on Day 7, no additional visits are required on Day 5 or Day 6.

The administration of the morning dose on the EOT visit will be observed by site staff/delegate and should be aligned with the timing of blood collection for PK analyses at EOT (SoA, Section 1.3).

For all doses, the timing of dose administration should be recorded in the Study Medication Diary.

If a participant misses a dose of the study intervention, then the following guidance should be followed:

- If ≤ 10 hours from the time the missed dose should have been taken, the missed dose should be taken, and the normal dosing schedule (ie, Q12H) resumed.
- If >10 hours from the time the missed dose should have been taken, the missed dose should be skipped, and the normal dosing schedule (ie, Q12H) resumed. The participant should not double the next dose to compensate for what has been missed.

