9.4.2 Safety Endpoints

A description of safety measures is contained in Section 8.3 and Section 8.4. The analysis of safety results is described in Section 9.6.2.

The safety analysis endpoints include:

- The proportion of: 1) participants with at least 1 AE; 2) participants with at least 1 drug-related AE; 3) participants with at least 1 SAE; 4) participants with at least 1 serious and drug-related AE; 5) participants who discontinued study intervention due to AE; 6) participants who discontinued study intervention due to a drug-related AE; and 7) participants with AE(s) leading to death. The AE reporting period is from the time of randomization through 14 days following cessation of treatment. Additional reporting periods will be used as appropriate (eg, throughout the study for SAE).
- Events of Clinical Interest specified in Section 8.4.7.

Predefined Limits of Change (PDLC) in Laboratory Parameters

For the summaries of laboratory tests, participants must have both a baseline and post-randomization on-treatment measurement to be included. Participants' laboratory values (based on their most abnormal laboratory test values, in the direction of interest, while on study intervention) will be classified as to whether or not they fall outside of the PDLC and are worse in grade (ie, more abnormal in the direction of interest) than at baseline. The criteria will be adapted from the DAIDS table for Grading the Severity of Adult and Pediatric Adverse Events, JUL 2017, version 2.1. A listing of the participants who meet the criteria will also be provided.

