9.6.2 Statistical Methods for Safety Analyses

Safety and tolerability will be assessed by clinical review of all relevant parameters including AEs, laboratory values and vital signs.

The analysis of safety results will follow a tiered approach as shown in [Table 6](#). The tiers differ with respect to the analyses that will be performed. For this protocol, only ECIs are considered Tier 1 events. AEs (specific terms as well as system organ class terms) and events that meet PDLCs in laboratory values or vital signs will be classified as belonging to "Tier 2" or "Tier 3" based on the number of events observed.

Tier 1 Events

Safety parameters or AEs of special interest that are identified a priori constitute "Tier 1" safety endpoints that will be subject to inferential testing for statistical significance with p-values and 95% CIs to be provided for between-treatment differences in the proportion of participants with events; these analyses will be performed using the unstratified Miettinen and Nurminen method [Miettinen, O. 1985], an unconditional, asymptotic method. Since the stratification factors are not considered to be related to safety endpoints, they will not be included as stratification factors in the safety analyses.

Tier 2 Events

Tier 2 parameters will be assessed via point estimates with 95% CIs provided for differences in the proportion of participants with events (also via the Miettinen and Nurminen method [Miettinen, O. 1985]).

Membership in Tier 2 requires that at least 4 participants in at least one treatment group exhibit the event. The threshold of at least 4 events was chosen because the 95% CI for the between-group difference in percent incidence will always include zero when treatment groups of equal size each have less than 4 events and thus would add little to the interpretation of potentially meaningful differences. Because many 95% CIs may be provided without adjustment for multiplicity, the CIs should be regarded as a helpful descriptive measure to be used in review, not a formal method for assessing the statistical significance of the between-group differences in AEs and predefined limits of change.

In addition to individual events that occur in 4 or more participants in any treatment group, the broad AE categories consisting of the proportion of participants with any AE, a drug-related AE, a serious AE, an AE which is both drug-related and serious, and discontinuation due to an AE will be considered Tier 2 endpoints.

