9.9.3 Sample Size and Power Calculations for Safety Analyses (Part 2)

Part 1 (Phase 2) and Part 2 (Phase 3) of the study will be combined for the final analysis of safety endpoints. The planned sample size for safety analysis will be 850 for each of a MK-4482 selected dose group and placebo group. The probability of observing at least 1 of a particular type of AE in this study depends on the number of participants treated and the underlying percentage of participants with an AE in the study population. If the underlying incidence of an AE is 1%, there is >99.9% chance of observing at least 1 AE among 850 participants in the treatment group. If no AE of that type is observed among the 850 participants in any treatment group, this study will provide 97.5% confidence that the underlying percentage of participants with the AE is <0.44 (1 of every 231 participants).

[Table 10](#) summarizes the percentage point differences between the 2 treatment groups that could be detected with 90% probability for a variety of hypothetical underlying incidences of an AE. These calculations assume 850 participants in each group and are based on a 2-sided 5% alpha level. The calculations are based on Farrington and Manning [Farrington, C. P. and Manning, G. 1990]. No multiplicity adjustments were made.

Table 10 Differences in Incidence of AE Rates Between the 2 Treatment Groups That Can be Detected With a ~90% Probability (Assuming 2-sided 5% Alpha Level with 850 Participants in Each Group)

Incidence of Adverse Event		Risk Difference
Placebo (%)	MK-4482 (%)	Percentage Points
1.0	3.3	2.3
5.0	9.1	4.1
10.0	15.3	5.3
20.0	26.7	6.7
30.0	37.5	7.5
40.0	47.8	7.8

Incidences presented here are hypothetical and do not represent actual adverse experiences in either group. Calculations are based on Farrington and Manning [Farrington, C. P. and Manning, G. 1990]

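### Serious-event and fatal-event safety totals include COVID-19 progression, with no summary that excludes it, so a benefit on hospitalization could hide other serious harm

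*Combined protocol and SAP*

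**What the plan says.** **Reporting.** The heading of 8.4.6 reads "Disease-related Events and/or Disease-related Outcomes Not Qualifying as AEs or SAEs". Its text takes the other direction for hospitalizations and deaths: "From the time of randomization through 14 days following cessation of study intervention, these events must be reported as described in Section 8.4.1". Section 8.4.1 makes no exception for endpoint events: "From the time of intervention randomization through 14 days following cessation of study intervention, all AEs, SAEs, and other reportable safety events must be reported". After that window the events are still assessed, but "they must only be reported to the Sponsor within 24 hours as new SAEs if there is evidence to suggest a causal relationship". Appendix 3 (10.3.1), in its list of events that do not meet the AE definition, sends the reader to 8.4.6 for exceptions. The text of 8.4.6 states none for the period up to 14 days after treatment.

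**Analysis.** Section 9.4.2 sets the window: "The AE reporting period is from the time of randomization through 14 days following cessation of treatment". Within it, the section counts participants with any AE, any SAE, discontinuation due to an AE and AEs leading to death, among others. Section 9.6.2 places in Tier 2 "the broad AE categories consisting of the proportion of participants with any AE, a drug-related AE, a serious AE", together with events both serious and drug-related and discontinuations. Each gets a 95% interval that the section calls descriptive. Table 6 repeats these rows, but has no row for AEs leading to death. None of the three places gives a version without COVID-19 progression.

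**Practice in the program.** Section 4.3.3 reports that COVID-19 was the most common AE resulting in death in the companion hospitalized study. Disease progression is therefore coded as an AE in this program.

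**The concern.** Within the AE window, the any-SAE total adds together two things that can move in opposite directions: COVID-19 hospitalizations and deaths, which the drug is meant to reduce, and any serious harm that the drug causes. If the drug works, the first falls and can offset a rise in the second. The fatal-AE total has the same structure. Any AE is affected less directly, because nonserious events also feed it.

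Even without any benefit, disease events add background variation that makes a modest excess of other serious events harder to see.

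The efficacy side does make this separation: 9.6.1 and Table 5 prespecify an analysis of COVID-related hospitalization or death. The safety side has no counterpart.

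The conflict between the heading of 8.4.6, its text and Appendix 3 is a separate problem. Sites could reasonably differ on whether an endpoint hospitalization is an SAE, which would make the content of these totals uncertain.

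**Working it through.** **1. Overlap of the two windows.** Section 8.1.8.1 says: "For participants that begin dosing in the morning on Day 1, the EOT visit will occur on Day 5". Its other start times put the last dose on Day 6 or Day 7. Adding 14 days closes the AE window on Day 19, 20 or 21, whereas the endpoint runs to Day 29. The documents do not give the share *w* of endpoint events that fall inside the window, so *w* is an assumption, taken here from 0.5 to 1.

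**2. The plan's own figure.** Section 9.9.3 and Table 10 list "differences between the 2 treatment groups that could be detected with 90% probability for a variety of hypothetical underlying incidences of an AE", with 850 per group and two-sided 5%. With d = p₂ − p₁,

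power = Φ[(d − 1.96·s₀)/s₁], s₀ = √(2p̄(1−p̄)/n), s₁ = √((p₁(1−p₁)+p₂(1−p₂))/n).

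For 1.0% vs 3.3%: d = 0.023, s₀ = 0.00704, s₁ = 0.00701, so power = Φ(1.31) = 90.5%. All six rows of Table 10 come out between 90% and 91%, so the table is reproduced.

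**3. Add the disease events.** Inputs:
- *e*: the design rates in 9.9.1 (12% placebo, 6% drug) or the Part 1 rates in the same section (5.4%, 4.1%).
- *t*: hypothetical non-disease SAEs of 1.0% placebo and 3.3% drug, borrowed from the first row of Table 10, which describes generic AEs.
- n = 850 per arm, with disease and non-disease events independent (assumption).

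Total any-SAE rate per arm = 1 − (1 − e·w)(1 − t).

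- 12% vs 6%, w = 1: placebo 1 − 0.88×0.99 = 12.9%; drug 1 − 0.94×0.967 = 9.1%.
- 12% vs 6%, w = 0.5: placebo 1 − 0.94×0.99 = 6.9%; drug 1 − 0.97×0.967 = 6.2%.
- Part 1 rates, w = 1: placebo 1 − 0.946×0.99 = 6.3%; drug 1 − 0.959×0.967 = 7.3%.

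The last column is the probability that a 95% comparison of the two totals excludes zero on the side of harm.

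| Disease events (placebo vs drug) | w | Any-SAE total (placebo vs drug) | Chance of showing the excess |
|---|---|---|---|
| excluded | – | 1.0% vs 3.3% | 90.5% |
| 12% vs 6% | 1 | 12.9% vs 9.1% | <0.1% |
| 12% vs 6% | 0.75 | 9.9% vs 7.7% | 0.02% |
| 12% vs 6% | 0.5 | 6.9% vs 6.2% | 0.5% |
| 5.4% vs 4.1% (Part 1) | 1 | 6.3% vs 7.3% | 11% |
| 12% vs 12% (no benefit) | 1 | 12.9% vs 14.9% | 23% |

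**4. Break-even.** The non-disease SAE rate on drug that just equalises the totals is 1 − (1 − placebo total)/(1 − e·w):
- 12% vs 6%, w = 1: 1 − 0.8712/0.94 = 7.3%, an excess of 6.3 points over 1.0%.
- 12% vs 6%, w = 0.5: 1 − 0.9306/0.97 = 4.1%, an excess of 3.1 points.
- Part 1 rates, w = 1: 1 − 0.9365/0.959 = 2.3%, an excess of 1.3 points.

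No such calculation is possible for any AE, because the documents give no any-AE rate.

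**The case against.** **These are not the primary safety endpoints.** A reader might infer that the primary safety comparison itself is compromised. The documents do not support that. Section 3 names AEs and AEs leading to discontinuation of study intervention as the primary safety endpoints. SAEs and fatal AEs are further endpoints in 9.4.2, and the calculation above speaks only to any SAE. This stands.

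**No formal test is involved.** At full capture and 12% vs 6%, the total would significantly favour the drug about 70% of the time, and a reader might call that a wrong safety conclusion. Section 9.6.2 tests only ECIs and treats Tier 2 intervals as an aid to clinical review. This also stands, although a descriptive interval that points the wrong way still informs that review.

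**The endpoint is all-cause.** A toxicity admission of at least 24 hours is itself an endpoint event, so 12% vs 6% is not purely disease. This is correct. The rates serve as an assumption, and the lower values of *w* also show the effect of a smaller disease component.

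**Other displays exist.** Drug-related rows, SOC and preferred-term rows, laboratory limits and ECIs are all reported, and the eDMC sees unblinded safety data. Comparing the all-cause and COVID-related efficacy analyses would also reveal an imbalance in other hospitalizations. These help, but none is a total of non-disease harm. The drug-related rows rest on case-by-case causality opinion, the SOC and term rows split diffuse harm, and the efficacy analyses cover only hospitalization and death.

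**The remedy also relies on attribution.** It does, so the all-inclusive rows must stay.

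**The supplemental SAP may cover this.** It is not available here. Section 9.6 defers other exploratory methods to it, but 9.6.2 does not defer safety methods.

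**Conclusion.** The point holds as a gap in the safety summaries. Through about Day 19 to 21, endpoint hospitalizations and deaths feed the any-SAE and fatal-AE totals, and no total excluding COVID-19 progression is planned. On the design rates, this could offset an excess of about 3 points (half capture) to 6 points (full capture) of other serious events. Table 10 puts about 90% probability on detecting an excess of 2.3 points from a 1.0% base.

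A reader might go further and infer that an effective drug would necessarily mask its own toxicity. The documents do not support that. The reversal of sign depends on the size of the benefit and on the share of events in the window. With Part 1 rates the total still points toward harm, although the chance of showing it is only about 11%. That loss of sensitivity appears in every scenario tabulated, including no benefit at all.

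The figures rest on independence, on the assumed range of *w*, on hypothetical non-disease rates, and on applying the Part 2 design rates to all 850 per arm, of whom about 75 come from Part 1. This is an inexpensive improvement that should be made; it does not invalidate the safety plan.

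**What to change.** 1. In 9.4.2, 9.6.2 and Table 6, add supplementary Tier 2 rows with 95% intervals for any AE, any SAE, discontinuation due to an AE and AE leading to death. Each should exclude events attributed to COVID-19 or its complications, not all primary-endpoint events, so that non-COVID hospitalizations stay visible.
2. Show these beside the all-inclusive rows. For AEs leading to death, the all-inclusive row must be added to Table 6 as well.
3. Classify events blinded, before database lock, from data already collected plus a prespecified list of COVID-19 terms. Section 8.2.3 records whether a hospitalization is related to COVID-19, and 8.2.4 records the COVID-19 contribution to death.
4. Reconcile the heading of 8.4.6, its text and the Appendix 3 cross-reference, so that sites report these events in the same way.

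The cost is SAP wording, a term list, a blinded classification step and a few table rows, with no new data collection. The small downside is that attribution to COVID-19 is a judgement, and a toxic event wrongly attributed to it would drop out of the new rows. That is why the all-inclusive rows stay.
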